17.4 Retention of Records

Essential documents should be retained until at least 2 years after the last approval of a marketing application and until there are no pending or contemplated marketing applications, or at least 2 years have elapsed since the formal discontinuation of the clinical development of the investigational product. These documents should be retained for a longer period, however, if required by the applicable regulatory requirements or by an agreement with the Sponsor.

The Sponsor will inform the PI/institution in writing of the need for record retention and will notify the PI/institution in writing when the trial-related records are no longer needed.

An investigator who withdraws from the responsibility of maintaining study records or wishes to move them to a new location has the obligation to place them in safekeeping and to inform the Sponsor of their location.

18.0 Analytical Plan

All statistical processing will be performed using SAS[®] version 9.3 or later, unless otherwise stated. All statistical tests will be two-sided and interpreted at a 5% significance level.

Descriptive statistics (i.e., mean, standard deviation, median, minimum, maximum, etc.) will be provided for all continuous variables; frequencies and percentages will be presented for incidence and categorical variables. For parameters measured over time, observed values and changes from Baseline will be described for each time point.

The clinical cure and mycological eradication rates will be described by baseline *Candida* species, when the number of isolates per species allows.

All analyses will be presented by treatment group. Unless otherwise stated, data will be analyzed as is with no imputation. No adjustment for multiplicity will be employed.

A Statistical Analysis Plan (SAP) describing all statistical analyses in detail will be provided as a separate document. The SAP will be finalized prior to unblinding of the study treatments.

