9.2 Secondary Endpoints

Efficacy as measured by:

- The percentage of subjects with mycological eradication (negative culture for growth of *Candida* species) at the TOC visit
- The percentage of subjects with clinical cure and mycological eradication (responder outcome) at the TOC visit.
- The percentage of subjects with complete resolution of symptoms at the Follow-up (FU) visit.
- The percentage of subjects with clinical improvement (partial or complete resolution of signs and symptoms with total composite score no greater than 1) at the TOC visit.
- The absolute change in signs and symptoms score from Baseline to TOC and FU visits.

Safety and tolerability as measured by:

- Adverse events (AEs), vital signs, physical examination, treatment discontinuation and safety laboratory tests

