3.2.2. Secondary Efficacy Endpoints

Efficacy as measured by:

- The percentage of subjects with mycological eradication (negative culture for growth of *Candida* species) at the TOC visit;
- The percentage of subjects with clinical cure and mycological eradication (responder outcome) at the TOC visit;

- The percentage of subjects with complete resolution of symptoms at the Follow-up (FU) visit;
- The percentage of subjects with clinical improvement (partial or complete resolution of signs and symptoms with total composite score no greater than 1) at the TOC visit;
- The absolute change in signs and symptoms score from Baseline to TOC and FU visits.

Safety and tolerability as measured by:

- Adverse events (AEs);
- Vital signs;
- Physical examination;
- Treatment discontinuation;
- Safety laboratory tests.

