Unless otherwise specified, baseline will be defined as the last non-missing assessment prior to or on the date (and time if appropriate) of the first dose of study drug. Change from baseline is defined as: post-baseline value – baseline value.

The study day will be calculated as follows:

If the assessment date occurs on or after the date of the first dose of study drug:

$$\text{Study day} = \text{assessment date} - \text{first dose date} + 1.$$

If the date of interest occurs before the date of the first dose of study drug:

$$\text{Study day} = \text{assessment date} - \text{first dose date}$$

There is no study day 0.

All analyses will be conducted using SAS Version 9.3 or higher. All statistical tests will be two-sided and interpreted at a 5% significance level.

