8.1.1. Primary Analysis

The primary efficacy analysis will be performed on the mITT set at the TOC visit and will compare the proportion of subjects, in the treatment and placebo groups, who have a clinical cure at the TOC visit.

The number and percentage of subjects with clinical cure at the TOC visit will be presented by treatment group. A Cochran Mantel Haenszel (CMH) test adjusted for site and diabetes mellitus diagnosis (Yes or No) will be performed to assess the statistical significance of a difference between treatment groups in the primary efficacy analysis. Mathematically stated:

$$\begin{aligned} H_0: \text{TOC Clinical Cure Rate Oral ibrexafungerp 300-mg dose} &= \text{TOC Clinical Cure Rate Placebo} \\ H_1: \text{TOC Clinical Cure Rate Oral ibrexafungerp 300-mg dose} &\neq \text{TOC Clinical Cure Rate Placebo} \end{aligned}$$

The p-value, odds ratio and 95% confidence interval will be presented in the ibrexafungerp 300-mg treatment arm compared to the placebo arm. Missing data for clinical outcome will be imputed using the NRI method described in Section 4.4. Additional summarizations will be performed by Candida Species of the baseline yeast, and the same inferential analysis will be performed, as appropriate.

The same inferential analysis employing the same methods as for the primary analysis will be performed for the ITT set and PP set to assess clinical cure at TOC visit. Missing data for clinical outcome will be imputed using the NRI method described in Section 4.4. No adjustment of type I error will be performed as these analyses are considered supportive to the primary analysis.

A sensitivity analysis using the mITT set will be performed where subjects with the imputed clinical outcome using the NRI method at TOC visit will be removed from the analysis.

Two subgroup analyses will be performed depending on Body Mass Index category ($\leq 35 \text{ kg/m}^2$ or $> 35 \text{ kg/m}^2$).

Analysis of time to resolution of signs and symptoms after initiation of study drug will use Kaplan-Meier method to estimate the median resolution time and its 2-sided 95% confidence intervals (CIs) based on the ITT, mITT, and PP sets. The time to resolution of signs and symptoms after initiation of study drug is defined as time (days) from first dose of study medication to the first resolution of signs and symptoms. Subjects who discontinued early will be censored at the last available assessment.

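### Six secondary efficacy tests are each read at two-sided 5% with no family-wise control, no gate on the primary test and no statement that their p-values are nominal

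*Protocol*

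**What the plan says.** Protocol section 18.0, repeated in the synopsis, sets two-sided 5% for all tests and adds: "No adjustment for multiplicity will be employed". SAP section 4 repeats the level: "All statistical tests will be two-sided and interpreted at a 5% significance level".

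Protocol section 9.2 and SAP section 3.2.2 list the same five secondary efficacy endpoints in the same order:

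- mycological eradication at TOC
- the responder outcome (clinical cure plus eradication) at TOC
- symptom resolution at FU
- clinical improvement at TOC
- "The absolute change in signs and symptoms score from Baseline to TOC and FU visits"

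SAP section 8.2.5 analyses the last item as two endpoints, one per visit, each with its own p-value. Protocol section 18.6.2 and SAP sections 8.2.1 to 8.2.5 plan inferential tests for all of them.

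The SAP's only sentence on type I error is in section 8.1.1: "No adjustment of type I error will be performed as these analyses are considered supportive to the primary analysis". It concerns the ITT and PP analyses of the primary endpoint, not the secondary endpoints. SAP section 11 lists changes from the protocol and does not mention multiplicity, so the protocol's statement stands.

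**The concern.** This is a Phase 3 trial in what protocol section 7.1 describes as a pivotal programme, and efficacy on mycological and clinical outcomes is a stated secondary objective. Six p-values will be produced and, under the general rule, each is read against 5%. The plan does not say whether a secondary result counts if the primary test fails, in which order the secondaries are read, or whether their p-values are descriptive only.

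What is at stake is the standing of the secondary results. A significant p-value for eradication or the responder outcome could be presented as a confirmed finding, although nothing limits the chance that at least one of six such findings is false. The primary conclusion is not at stake.

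**Working it through.** **1. The plan's own figure.** Protocol section 18.1 and SAP section 4.1 assume cure rates of 50% and 30%, 2:1 allocation, 90% power, two-sided 5% and a Pearson chi-squared test. The pooled rate is (0.3 + 2 × 0.5)/3 = 0.4333, so the placebo group needs

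n = [1.960 × √(1.5 × 0.4333 × 0.5667) + 1.2816 × √(0.21 + 0.25/2)]² / 0.20² = (1.1895 + 0.7418)² / 0.04 = 93.2, rounded up to 94.

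The total is 94 + 188 = 282, as stated, with 90.2% power. The full 5% is therefore assigned to one primary test. The documents state no family-wise figure for the secondaries to reproduce.

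**2. Number of tests.** Four endpoints at one visit each plus one at two visits make six tests.

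**3. Independence.** If all six null hypotheses are true:

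- p below 0.05 in either direction: 1 − 0.95⁶ = 0.265
- false findings favouring ibrexafungerp only (2.5% per test): 1 − 0.975⁶ = 0.141

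**4. Correlated tests.** The documents give no correlation between the test statistics, so a range is assumed. For six equicorrelated z-tests with common correlation ρ, c = 1.96 and X standard normal,

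P(at least one) = 1 − E[{Φ((c − √ρ·X)/√(1−ρ)) − Φ((−c − √ρ·X)/√(1−ρ))}⁶].

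Dropping the second Φ term gives the one-direction version. By numerical quadrature:

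| Assumed ρ | Either direction | Favouring ibrexafungerp only |
|---|---|---|
| 0 | 26.5% | 14.1% |
| 0.3 | 24.1% | 12.2% |
| 0.5 | 20.7% | 10.4% |
| 0.7 | 16.4% | 8.2% |
| 0.8 | 13.9% | 6.9% |
| 0.9 | 10.8% | 5.4% |

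The matching benchmarks for confirmatory claims are 5% and 2.5%.

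**5. Overlap built in.** A null simulation let the endpoints share components as the SAP defines them. It assumed 195 and 98 subjects, null response rates of 30% to 45%, latent correlations of 0 to 0.7 and 6,000 runs per setting. It gave 19.4% to 22.6% in either direction.

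**6. Sensitivity to the count.** With the last bullet taken as one test (five in all): 22.6% under independence, 14.8% at ρ = 0.7. With the FU eradication test of SAP section 8.2.1 added (seven in all): 30.2% and 17.8%. By-species tests and repeats in other analysis sets are not counted.

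**7. What control would do.** In a fixed sequence gated on the primary, a false rejection requires rejecting the first true null hypothesis in the order, which is tested at 5%. The error over the primary and all six secondaries is therefore at most 5% under any correlation. Bonferroni over the six (0.05/6 = 0.0083 each) gives 1 − (1 − 0.0083)⁶ = 4.9% under independence.

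**The case against.** The strongest reply is that this is a disclosed choice. There is one primary endpoint, mITT is named as the primary population, and no interim analysis is planned. A reader might infer that the trial's type I error is inflated, or that the plan breaks a 5% promise. The documents support neither: the primary test keeps its full 5%, and 5% is set per test, never for the family of secondaries. A reader might also infer that the sponsor means to claim success on a secondary if the primary fails. Nothing says so; the plan is only silent on that case. All of this stands.

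The size also depends on assumptions. Independence is implausible by construction:

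- Overall success is a subset of both cure and eradication (SAP section 8.2.2).
- Clinical improvement and the TOC score change use the same composite score (SAP sections 8.2.4 and 8.2.5).
- A symptom-free subject with no signs rated at FU is given a composite of zero (SAP section 8.1), which ties two FU endpoints together.

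The figures also require all six null hypotheses to be true. That stands too.

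Disclosure does not close the gap, however. It would if the plan also said that the secondary p-values are nominal. Instead, every test is to be interpreted at 5%, and the word supportive is reserved for the ITT and PP analyses.

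A fixed sequence is one option among several; Holm or Bonferroni would also control the error. Nothing says that the listed order is a ranking.

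**Conclusion.** The point holds as a gap in how the secondary results are to be read, not as an error in the primary analysis. Six secondary tests at two-sided 5% have no family-wise control, no gate on the primary and no nominal label, so as written their p-values cannot carry confirmatory statements.

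The table under working gives the size. No single figure should be quoted as the trial's error rate: 26.5% is the independence case, the value falls below 16% once the correlation passes about 0.7, and all values rest on six true null hypotheses. Even at a correlation of 0.9 the figures (10.8% and 5.4%) are about twice their benchmarks. If the secondary p-values are reported as nominal, no error is made, but neither document says they will be.

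**What to change.** Before unblinding, which is when protocol section 18.0 requires the SAP to be final, add one paragraph to the SAP. List it in SAP section 11 as a change from protocol section 18.0 and the synopsis. It should say:

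- If the primary mITT test is significant at two-sided 5%, the secondaries are tested in the mITT set in a fixed order, each at two-sided 5%, stopping at the first non-significant result.
- The order in protocol section 9.2 and SAP section 3.2.2 can serve, with the last item split: eradication at TOC, responder outcome at TOC, symptom resolution at FU, clinical improvement at TOC, score change at TOC, score change at FU. The sponsor may prefer another order, provided it is fixed in advance.
- p-values after the stopping point are nominal, as are those for FU eradication, by-species analyses and the ITT and PP sets.

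The responder outcome would be the second step. SAP section 8.2.2 drops undetermined subjects for it, while the other categorical secondaries use non-responder imputation, so that handling should be confirmed before the order is fixed.

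The cost is one paragraph and one line in section 11. Primary power is unchanged. The downside is that endpoints after a failed step are nominal only.

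If the sponsor wants no confirmatory secondary claims, the minimum change is one sentence stating that all secondary p-values are nominal.

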18.1 Sample Size Determination

The primary endpoint of the study is the percentage of subjects achieving a clinical cure at the TOC visit. Assuming clinical cure rates of 50% and 30% for ibrexafungerp and placebo administered in a 2:1 ratio, respectively, approximately 282 subjects will provide 90% power to detect a difference between ibrexafungerp and placebo based on a Pearson's Chi-squared test with a Type 1 error rate of 5%. Because it is expected that approximately 20% of subjects may not have a mycological culture-confirmed infection at Baseline and approximately 10% may withdraw early from the study, an additional 84 subjects are added for a total of 366 subjects (244 subjects randomized to ibrexafungerp and 122 subjects, to placebo).

18.2 Analysis Populations

The study populations to be used in the analyses are defined as follows:

Intent-to-Treat (ITT) Population: All randomized subjects.

Modified Intent-to-Treat (mITT) Population: All randomized subjects who have a positive culture for *Candida* species at Baseline.

Per-Protocol (PP) Population: All mITT subjects who have completed the study drug treatment AND who have a TOC evaluation.

Safety Population: All randomized subjects who received at least one dose of study drug and who have at least one post-Baseline evaluation.

18.3 Subject Disposition, Discontinuation, and Baseline Data

Subject disposition in terms of the number and percentage of subjects enrolled by site will be tabulated. The number of subjects randomized, number completing the study, and reasons for discontinuation will be summarized by treatment group. Subject demographics and baseline characteristics such as age, race, ethnicity, sex, weight, height, body mass index, region (if applicable) and other relevant parameters will be tabulated by treatment group.

Baseline is defined as the last non-missing assessment prior to the date (and time if appropriate) of the first dose of study drug. Change from baseline is defined as: post-baseline value – baseline value.

18.4 Handling of Missing Data, Dose Adjustments, and Early Withdrawals

For the efficacy analyses, subjects who do not have a TOC (Day 8-Day 14) assessment will be assigned as treatment failures. For subjects who withdraw from the study early, every effort will be made to collect TOC visit information at the point of withdrawal.

18.5 Prior and Concomitant Medications

Prior and concomitant medications will be coded using the World Health Organization Drug Dictionary terminology. The number and percentage of subjects taking each medication before and after the first dose of study drug will be tabulated by treatment group. Medications taken and stopped prior to the first dose of study drug will be considered prior medications. Medications started on or before the FU visit date with missing stop dates or stop dates after the first dose of study drug will be considered concomitant medications.

18.6 Efficacy

18.6.1 Efficacy Assessments

The primary efficacy endpoint of the study is the percentage of subjects with clinical cure (complete resolution of signs and symptoms) at the TOC visit. Secondary efficacy endpoints include the percentage of subjects with mycological eradication (negative culture for growth of *Candida* species) at the TOC visit, the percentage of subjects with clinical cure and mycological eradication at the TOC visit, the percentage of subjects with complete resolution of symptoms at the FU visit, and the percentage of subjects with clinical improvement (partial or complete resolution of signs and symptoms with a total composite score no greater than 1) at the TOC visit and the absolute change in signs and symptoms score from Baseline to TOC and FU visits.

The following treatment outcome definitions will be used for the assessment of efficacy relative to baseline:

Clinical Outcome

- Clinical cure: Complete resolution of signs and symptoms of vulvovaginal infection without need for further antifungal treatment. Specifically, for complete resolution, any sign or symptom should be absent (score = 0) by the TOC visit.
- Clinical failure: No response to therapy or incomplete resolution of signs and symptoms or need for additional vulvovaginal or systemic antifungal therapy. If the

subject receives or self-administers topical drug therapy for the treatment of vulvovaginal irritation/pruritus such as topical analgesic or corticosteroid after completing treatment with the study drug and before the TOC visit, the subject is considered a clinical failure.

Mycological Outcome

- Mycological eradication: A subject with negative culture for *Candida* species.
- Mycological persistence: A subject with a positive culture for *Candida* species.

18.6.2 Efficacy Analyses

The efficacy analyses will be conducted using the mITT (primary analysis population), ITT and PP populations to evaluate ibrexafungerp vs. placebo.

The primary endpoint, percentage of subjects with clinical cure at TOC, will be analyzed using a Cochran Mantel Haenszel (CMH) test adjusted for site; the p-value and 95% confidence intervals will be presented. Missing Day 8-Day 14 (TOC) data for the primary endpoint will be imputed as failures in the analysis. A sensitivity analysis will be performed where subjects with missing values will be removed from the analysis. All other data will be analyzed as is with no imputation.

For other continuous efficacy endpoints, a two-way analysis of variance (ANOVA) model will be used including effects for treatment and site; p-values and 95% confidence intervals will be presented. For other categorical endpoints, the CMH test adjusted for site will be performed, and p-values and 95% confidence intervals will be presented.

18.7 Safety

18.7.1 Safety Assessments

Safety will be evaluated throughout the study, including the following parameters: AEs, treatment discontinuations, physical examination, vital signs, safety laboratory tests, and prior and concomitant medications.

AEs will be recorded and reviewed at all scheduled and unscheduled study visits from the time the Informed Consent Form is signed. An abbreviated physical examination, including general appearance and an overall examination of body systems, will be conducted at Screening and at the TOC visit. Vital signs, including blood pressure (systolic and diastolic), heart rate, respiratory rate and body temperature will be measured at the Screening and TOC visits, and at unscheduled visits, if needed. Safety laboratory tests

(hematology and blood chemistry) will be measured at Screening, at the TOC visit and at unscheduled visits, if needed. All prior and concomitant medications taken before Baseline (Day 1) through the TOC visit will be recorded. Only the use of antifungal medications, vaginal (topical) medications, antibiotics for any reason or any other medications to treat an AE will be recorded after the TOC visit through the last study visit (FU).

Safety procedures are described in [Section 14.0](#) and safety assessments are described in [Section 16.0](#).

18.7.2 Analyses

Safety analyses will be conducted using the safety population.

AEs will be coded using the Medical Dictionary for Regulatory Activities (MedDRA) Version 19.1 or higher. The incidence and severity of treatment-emergent AEs and SAEs and their relationship to treatment will be summarized by system organ class and preferred term. The percentage of subjects who discontinued study treatment and the reasons for discontinuation will be summarized by treatment group.

Safety laboratory evaluations and vital signs will be summarized as observed values and as changes from Baseline. In addition, shifts (with respect to the reference range) from Baseline will be presented by treatment group for laboratory tests.

19.0 Ethics and Protection of Human Patients

19.1 Ethical Conduct of the Study

The study will be conducted in accordance with the protocol, the ethical principles established by the Declaration of Helsinki (as amended in Fortaleza, Brazil, October 2013), the International Conference on Harmonisation (ICH) Good Clinical Practice (GCP) Guidelines, the US Code of Federal Regulations (CFR) sections that address clinical research studies, applicable European Union regulations and/or other national and local ethical and legal requirements, as applicable.

19.2 Institutional Review Board/Ethics Committee Review

The PI or CRO must provide the IRB/EC with all appropriate materials, including a copy of the subject ICF. The study will not be initiated until the PI or CRO obtains written approval of the protocol and the subject ICF from the appropriate IRB/EC, and copies of these documents are received by the Sponsor. Appropriate reports on the progress of this study will be made by the PI to the IRB/EC, medical monitor, and Sponsor in accordance

with applicable government regulations and in agreement with policy established by the Sponsor.

